ID: Pro00003376

View: 4.1 Research study methods: analysis Plan

1.0 * Please describe the analysis plan for the study (it is acceptable to refer to the sponsor/multi-site protocol for section if applicable):

Primary Data Analysis: We will use R version 3.4. **SA1:** To assess the feasibility of the current design to measure the effect of BLT on sleep related functional impairment in CPAP-treated individual with OSA. We will describe the following components of feasibility: recruitment and participant flow, adherence, data completeness and participant burden, and time course of treatment effects (e.g. do carry-over effects require a longer wash out period or suggest that a two-arm between-subject RCT design would be more appropriate?). Our main outcome analyses will employ multi-level linear mixed models with sleep related functional impairment and depression as the dependent variable, treatment block (BLT vs. sBLT) as predictor of interest, treatment sequence as a covariate, and subject intercept as a random effect.

Bivariate and colinear relationships will be assessed and proxy variables may be created to adjust for variables that are strongly biased (>3 SD from the mean) or highly collinear with a model-pertinent variable. Covariates we will be assessing include demographics (age, sex, race), comorbid conditions, lifestyle behaviors (smoking, alcohol use, substance use), adherence to BLT treatment, adherence to CPAP, medications for treatment of depression, use of hypnotic medications, and healthcare utilization (number of inpatient/ER visits within the past year).

SA2: to test the effects of bright light therapy on sleep related functional impairment, quality of life and CPAP-resistant symptoms of sleepiness and depression during the four-week active treatment portion of the eight-week crossover study, compared to the four-week sham treatment portion. These exploratory analyses will include bivariate analyses comparing patient outcomes between treatment and sham time periods by utilizing repeated measures ANOVA for quality of life and the Friedman test for categorical variables. We will conduct multi-level mixed effects models of each outcome while adjusting for covariates as listed in the primary aim.

SA3: to test the effect of BLT on CPAP resistant daytime symptoms through **reduced variability of circadian rhythms**, assessed via actigraphy. In order to test this, we will first generate relevant rest-activity rhythms (RAR) measures from minute by minute actigraphy measurements collected over seven days: RAR *height* (amplitude, mesor), *timing* (up-mesor, acrophase, down-mesor). *RAR parameters will be modelled from minute-to-minute actigraphy count data using a five-parameter extended sigmoidally transformed cosine model with an anti-logistic function. This model has been shown to fit human RAR data more effectively than a standard cosine curve⁴⁹. The extended cosine model also provides a measure of how well the observed activity data are fitted by the 24-h rhythm model known as the pseudo-F statistic; lower values indicate poorer model fit and suggest an erratic or variable rhythm⁵⁰.* Bivariate analyses of the effect of BLT on variability of circadian rhythms parameters will be compared using repeated measures ANOVA. We will conduct multi-level mixed effects models of each outcome while adjusting for covariates as listed in the primary aim.

ID: Pro00003376

View: 5 Sub-Studies

1.0 * Is there a sub-study or are there sub-studies associated with this study?
There is no sub-study associated with this study.

ID: Pro00003376

View: 6 Study Population Summary

Study Population Summary

1.0 * What is the maximum number of subjects you plan to enroll at VAPHS?
25

2.0 * Do you plan on enrolling patients into different categories:
 Yes No

If yes, please explain:

This is a 2-arm cross-over study with each participant receiving both arms of treatment for 4 weeks each separated by one week of wash-out period to minimize carry over effects. The order of treatment is randomly assigned.

3.0 If this is a multi-site study, indicate the projected total subject accrual:
N/A

4.0 * Please provide a justification for the sample size:
Sample size strictly based on statistical power is not applicable in the proposed pilot trial. This study is mainly aimed at testing feasibility of the proposed design and intervention, rather than hypothesis testing through inferential statistics. The statistics and qualitative data obtained from the proposed pilot trial will be used to inform design adjustments in the subsequent large trial.

ID: Pro00003376

View: 6.1 Study Population

Study Population**1.0 * Check all that apply to describe your study population:**

Study Population

 Non-Veterans **Special Populations** **Veterans** Vulnerable populations Other**2.0 * Indicate the inclusion criteria for enrollment:**

- 1) Male or female veterans aged 45-65
- 2) Documented diagnosis of OSA, currently on CPAP or BiPAP with documented adherence (defined as wearing CPAP/BiPAP for >4h/ night on at least 75% of nights)
- 3) Excessive residual daytime sleepiness (Epworth score >/= 10)
- 4) Minimal sleep time, i.e. average total sleep time (TST)≥6 hours

3.0 * Indicate exclusion criteria for enrollment:

- 1) shift work
- 2) Travel across time zones in past month
- 3) Narcolepsy
- 4) Decompensated congestive heart failure (CHF)
- 5) Dementia, or bipolar disorder
- 6) Macular degeneration
- 7) Recent (within 3 months) lasik surgery or planned lasik surgery in the next 3 months
- 8) Taking medication that will cause photosensitivity to blue-green light spectrum wavelength
- 9) Poorly controlled diabetes (HgA1c>8%)
- 10) Active substance use disorder
- 11) Currently taking alertness-promoting agents such as Modafinil or stimulants
- 12) Current enrollment in another Greater than minimal risk study

4.0 If there are any age, ethnic, language, or gender-based exclusion criteria, including the exclusion of any pregnant or lactating women, or those of child-bearing potential, please provide justification:

N/A

5.0 Please specify why vulnerable subjects and/or special populations will not be enrolled:**6.0 With some exceptions as listed in VHA Handbook 1200.05, incompetent subjects cannot be enrolled in VAPHS approved research. Specify that you will not enroll incompetent subjects and the general rules to be used in making that determination:**

Incompetent subjects will not be enrolled.

ID: Pro00003376

View: 6.3 Study Population- Special Populations

Study Population

1.0 * Check all that apply to describe your study population:

Name

Employee and Student Subjects

Investigators Clinical Population

2.0 * Provide a justification for including these subjects:

[name] is a sleep provider clinician so she will recruit from her patients when appropriate. Some may be her own patients, but the majority will be other provider's patients. We have selected special populations in the event that any subject is from her own case load.

ID: Pro00003376

View: 6.3.2 Investigators clinical population

Investigators clinical population

1.0 * Please indicate how you will minimize the potential for them to feel coerced to participate. Discuss how the potential confusion in roles will be addressed:

The informed consent document emphasizes the investigator's conflict of interest and voluntary participation of the patient. [name] will emphasize that fact to the patient when they are potentially eligible to participate in this study.

ID: Pro00003376

View: 7 Risk/Benefit Assessment-Risks

Risk/Benefit Assessment-Risks**1.0 * Risk classification for this study (select one).**

Name

 Minimal Risk Greater than Minimal Risk**2.0 * Basis for making the above recommendation:**

The device used in this study, the Re-timer® glasses, is commercially available and in use by the general population, and is available without a prescription and individuals are not prevented from buying it, hence the level of risk incurred by the participant is not greater than what they may incur in daily life, as they could go online and buy it.

The light intensities used in this study are greater than most indoor light, but much dimmer than sunlight on a bright day.

The Re-timer® device is commercially available and not FDA-regulated because it is considered a minimal risk system, and is currently being used in a Michigan Medicine study in patients with postpartum depression.

3.0 * Describe the safety precautions that will be taken to minimize risks/harms:

Education about use of the study equipment. Instruction on proper home use for the BLT glasses will be provided by study staff.

Any issues will be addressed at each of the scheduled study visits.

In addition there will be a phone call to each subject 1 week after receiving the study glasses to address compliance and any issues they may be having.

During the assessments (both phone and in person), the participant will be directed to verbalize to the PI or research staff if they are having any discomfort and all research activity will be stopped if necessary.

Additionally, any issues will be addressed at each of the scheduled study visits.

If a participant responds to the questionnaires indicating that they are at risk for suicidality, the physician investigator will be consulted. Based on the information obtained, the PI or co-investigators will evaluate suicide risk and decide what level of care is sufficient in conjunction with participants' behavioral health clinician. If the participant does not have a behavioral health clinician, they will be referred to behavioral health for evaluation and treatment.

4.0 * Provide details regarding the nature of each risk using the area provided below:

Risk Name

[View](#) wearing bright light therapy glasses[View](#) Privacy and confidentiality[View](#) Wearing ActiWatch**5.0 * Do you plan on using the research answering service: Yes No**

If yes, please Upload the research answering service form:

6.0 If your study involves a treatment or intervention, please upload the Patient ID Card:[Patient ID card \(0.01\)](#)

ID: Pro00003376 View: 7.1 Risk/Benefit Analysis-Potential Benefits and Alternatives

Risk/Benefit Analysis-Potential Benefits and Alternatives

Describe any potential for direct benefits to participants in this study:

1.0 * Benefit to Subjects:

Hypothesis: The effect of BLT on CPAP resistant daytime symptoms will be exerted through increased regularity of circadian rhythms, assessed via actigraphy. At the completion of this project, we will have generated preliminary data critical to the design and implementation of a larger trial investigating the impact of BLT on CPAP-resistant symptoms of sleepiness and depression, leading to increased functional impairment in OSA patients. If proven effective, this intervention has the potential to improve the lives of many Veterans suffering from OSA who do not find full symptomatic relief with CPAP, by offering a non-pharmacological intervention that is safe, relatively inexpensive and whose implementation demands only a minimal degree of behavioral modification on the patient.

2.0 * Describe alternatives (research or non-research) that are available to subjects if they choose not to participate in this study:

not participate
other research opportunities
VAPHS Standard of Care (patient dependent)

ID: Pro00003376

View: 8 Methods of Recruitment and Retention

Recruitment Methods and Materials used for Retention**1.0 * Select recruitment methods used on this study:**

Name _____

Mail Campaign _____

Referral by independent source _____

Advertising such as fliers, letters, or ads (newspaper, TV, radio) _____

Web Site _____

Research registry _____

Selected from pre-existing records _____

Pre-existing relationship with participants _____

Other _____

If Other Methods Specify:

2.0 * Specify how subjects will be identified and how study eligibility will be determined:

We will request a waiver of HIPAA to review the CPRS records of veterans coming for a follow up appointment at the VAPHS Sleep Center. Those that are age 45-65 with a documented diagnosis of OSA and have a documented adherence to CPAP/BiPAP of at least 75% of nights and Epworth score > 10 according to their medical record, will be considered for screening. The clinician seeing (in person or by tele visit) the patient will be contacted by encrypted email asking if they agree to suggest to their patient that they may be eligible to participate in a research study. They can hand the patient (or mention) a brochure describing the study (IRB-approved). If (s)he is interested in participating, (s)he will have the option to undergo an in-person meeting or call the study research coordinator, whose contact information will be provided in the brochure, at another time so the research coordinator can answer any questions the subject may have about the study. There will be no cold calling of veterans who do not express interest in participating. Those who choose to meet in person will sign an informed consent. Those who would like to participate in the study will undergo remote consent over the phone.

Screening Procedures: Participant eligibility (see inclusion/exclusion criteria above) will be initially determined by the Inclusion and Exclusion Criteria document based on CPRS records. If there is criteria unable to be answered during the pre-screening process, this does not eliminate the potential participant. If eligible or potentially eligible based on the pre-screen, the participant will be invited to come in for on-site evaluation. After being consented, any unanswered questions from the Inclusion and Exclusion Criteria document will be asked. If confirmed to be eligible, the patient will continue. If not, the subject will be considered a screen fail and participation in the study will end.

3.0 * Provide the location (or locations) of the sites where participants will be recruited:
VAPHS sleep clinic**4.0 Please include information regarding any advertisements (print, TV, radio, etc) that will be used to recruit subjects including a general description of where this information will be posted:**

Approved brochure located in VAPHS Sleep Clinic

5.0 Please UPLOAD the documents that will be used for recruitment and an introductory statement or letter to accompany consent for those studies obtaining written informed consent using methods such as fax, email or mail (if applicable). Please also upload any

screening/recruitment questions that will be verbally asked of potential research subjects. Also, if you will be providing any retention materials, please upload them here.

| Name | Reviewer | Modified Date | Version Number |
|--|------------------|-------------------|----------------|
| APPROVAL RE_ Review_ Bright Light Therapy study brochure.pdf | [name] | 2/26/2020 1:33 PM | 0.01 |
| Bright-Light-Therapy_Research-study_brochure2.pdf | [name] | 2/26/2020 1:33 PM | 0.01 |

ID: Pro00003376

View: 9 Informed Consent

Informed Consent

1.0

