have demonstrated that short amounts (30-60 minutes) of daily light therapy in the morning effectively realigns individuals' circadian rhythms, leading to improvements in sleep duration, self-reported sleep quality, insomnia symptoms and fatigue ¹⁵. There is robust evidence that light is effective in acutely decreasing sleepiness and fatigue ^{34 35} and increasing alertness ^{36 37 38}. Moreover, light therapy is used alone or as adjuvant therapy in a growing number of psychiatric and neurodegenerative diseases, where alterations of sleep-wake cycles are often observed ³⁹. Despite the mounting evidence of the benefits of BLT for a number of symptoms and functional domains affected in patients with OSA, no study to date has explored its role for patients with sleep apnea.

Design Overview: This is a feasibility study for a within-subjects cross-over trial: eligible participants will undergo baseline assessments over one week, during which baseline measures, including actigraphy, will be collected. They will subsequently be randomized to one of two treatment sequences Bright Light Therapy-Sham Bright Light Therapy (BLT-sBLT) or sBLT-BLT for the total duration of 9 weeks (4 weeks in each treatment arm, plus one week of "wash-out period in between treatments). To avoid subjects potential awareness of placebo treatment (differences in light intensity between the active and sham treatment cannot be completely eliminated), subjects will be told that the study will test the effects of two different light intensities on the target symptoms. Participants will undergo a further final assessment at week 12, 4 weeks after completion of the treatment.

3.0 * Describe the study objectives. Please include primary aim and hypothesis, if applicable any secondary aims and hypotheses.

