SA1: to test the feasibility of Bright Light Therapy (BLT) to ameliorate sleep related functional impairment in CPAP-treated individuals with OSA. Hypothesis: BLT, delivered via therapy glasses, will have high rates of acceptance and adherence among Veterans with OSA who still experience residuals symptoms, despite adequate treatment with CPAP. We will use a cross-over design, where each participant will be exposed to active treatment and sham treatment in a randomize order. We will collect qualitative data from participants regarding the feasibility and acceptability of BLT to guide future testing and implementation of treatment. **SA2** (exploratory): to test the effects of bright light therapy on sleep related functional impairment, quality of life and CPAP-resistant symptoms of sleepiness and depression. Hypothesis: participants will demonstrate improvements in the variables of interest during the four-week active treatment portion of the eight-week crossover study, compared to the four-week sham treatment portion. We will also be able to detect potential treatment carryover effects and inform design decisions for a subsequent larger study. **SA3** (exploratory): to test whether the degree of circadian rhythms regularity (marker of re-alignment) during BLT mediates the effects of BLT on CPAP-resistant symptoms. Hypothesis: the effect of BLT on CPAP resistant daytime symptoms will be exerted through increased regularity of circadian rhythms, assessed via actigraphy. At the completion of this project, we will have generated preliminary data critical to the design and implementation of a larger trial investigating the impact of BLT on CPAP-resistant symptoms of sleepiness and depression, leading to increased functional impairment in OSA patients. If proven effective, this intervention has the potential to improve the lives of many Veterans suffering from OSA who do not find full symptomatic relief with CPAP, by offering a non-pharmacological intervention that is safe, relatively inexpensive and whose implementation demands only a minimal degree of behavioral modification on the patient.

4.0

*** Provide a summary of the background of the study, and explain how this research will contribute to existing knowledge. Describe previous studies that provides a basis to show that the proposed research can be carried out without undue risk to human subjects.**

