At the time of the on-site evaluation, a member of the study staff will obtain written informed consent and the study coordinator will administer study questionnaires and instruct subjects to wear the actigraph and complete a sleep diary for one week. If the participant is enrolling remotely, remote consent will be obtained over the phone and study materials, including an information sheet, the actigraph and sleep diary, will be mailed to the participant. At the end of the baseline assessment week, participants will return the actigraph and sleep log and will complete study questionnaires. Research staff will download actigraphy data and determine the time for administration of BLT based on habitual wake up time (average wake up time for baseline week). Participants will then be given a newly charged actigraph to wear for the following 4 weeks and the BLT glasses in person or mailed to them if they are doing visits remotely.

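### SA2 promises to detect carryover, but with at most 25 participants the sequence contrast can only estimate it, and imprecisely

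*Combined protocol and SAP*

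**What the plan says.** The study objectives (View 2, item 3.0) say under SA2, which is labelled exploratory: "We will also be able to detect potential treatment carryover effects and inform design decisions for a subsequent larger study". No carryover size, precision or power is attached.

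The analysis plan (View 4.1, SA1) introduces its list with "We will describe the following components of feasibility". One item is the time course of treatment effects, illustrated by the question "do carry-over effects require a longer wash out period or suggest that a two-arm between-subject RCT design would be more appropriate". The outcome model has treatment block as the predictor of interest, "treatment sequence as a covariate, and subject intercept as a random effect". It contains no separate carryover term.

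The Study Population Summary (View 6) caps enrolment at 25. It justifies the number by feasibility "rather than hypothesis testing through inferential statistics".

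Baseline scores will exist. The Design Overview describes a baseline week before randomisation, "during which baseline measures, including actigraphy, will be collected". The Research Procedures (View 4, item 1.0) add: "At the end of the baseline assessment week, participants will return the actigraph and sleep log and will complete study questionnaires". The visible model does not list the baseline score as a covariate.

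**The concern.** In a two-sequence, two-period crossover, carryover is estimated by comparing people between the two sequences, so it does not gain the within-person precision that the treatment comparison enjoys. With 25 people this is a small parallel-group comparison. The sequence contrast also mixes carryover with any treatment-by-period interaction and with chance imbalance between the groups.

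The pilot exists to inform the next trial, and whether to lengthen the washout or move to a parallel-group design is one of the questions it is meant to help answer. If the study is described as able to detect carryover, a null sequence effect may later be taken to mean that one week of washout was enough. At this sample size, a null result would be compatible both with no carryover and with a large one. The visible plan does not say how an inconclusive sequence effect would be read.

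**Working it through.** The documents give no power or precision figure for carryover, so there is none to reproduce. The check asks what the sequence contrast can deliver.

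**From the documents.** Maximum 25 participants (View 6); two sequences over two four-week periods (Design Overview); a model with treatment, sequence and a random subject intercept (View 4.1).

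**Assumed, because the documents are silent.** A 12 versus 13 split; no dropout; single-period outcome SD = 1; equal correlation ρ of 0.3 to 0.8 among baseline and both periods; two-sided 5% level; no other covariates. Carryovers of 0.5 and 1 SD are illustrations only.

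**Scale.** Let L be the carryover into period 2, in single-period SD units. The difference between sequences in the total of the two periods estimates L. The model's sequence coefficient estimates L/2.

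**Unadjusted contrast (23 df).** k = √(1/12 + 1/13) = 0.400. SE(L) = √(2(1+ρ)) × k. The half-width is 2.069 × SE, and power comes from the noncentral t distribution. At ρ = 0.5, for example, SE = √3 × 0.400 = 0.693 and the half-width is 1.43.

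| ρ | SE | 95% half-width | Power, L = 0.5 | Power, L = 1 |
|---|---|---|---|---|
| 0.3 | 0.645 | 1.34 | 11.5% | 31.8% |
| 0.5 | 0.693 | 1.43 | 10.6% | 28.2% |
| 0.7 | 0.738 | 1.53 | 10.0% | 25.5% |
| 0.8 | 0.760 | 1.57 | 9.7% | 24.3% |

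Eighty per cent power would need a carryover of about 1.9 SD (ρ = 0.3) to 2.2 SD (ρ = 0.8). Relaxing the test to a two-sided 10% level raises power only to 19.4–16.8% at 0.5 SD and 44.5–35.9% at 1 SD.

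**Adjusted for the baseline score (22 df).** SE(L) ≈ √(2(1+ρ) − 4ρ²) × k. This formula ignores the cost of chance baseline imbalance, so power is taken from simulation of the adjusted analysis.

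| ρ | SE (formula) | Half-width, formula | Half-width, simulated mean | Power, L = 0.5 | Power, L = 1 |
|---|---|---|---|---|---|
| 0.3 | 0.599 | 1.24 | 1.26 | 12% | 35% |
| 0.5 | 0.566 | 1.17 | 1.19 | 13% | 38% |
| 0.7 | 0.480 | 1.00 | 1.01 | 17% | 49% |
| 0.8 | 0.408 | 0.85 | 0.86 | 21% | 63% |

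By the formula, adjustment cuts the half-width by about 7% at ρ = 0.3 (1 − 1.24/1.34) and 46% at ρ = 0.8 (1 − 0.85/1.57).

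**If only 20 complete (10 versus 10).** The half-width is 1.51–1.78 SD unadjusted and 1.41–0.96 SD adjusted.

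**The case against.** The strongest reply is that the documents already limit the claim. SA2 is exploratory, the analysis plan says carryover will be described, and the sample-size section sets hypothesis testing aside. This stands, and it makes the point minor. It does not make the SA2 sentence true; it shows that the sentence is out of step with the rest of the plan.

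A second reply is that carryover is filed under the time course of treatment effects, which is wider than one model term, and that a final assessment four weeks after treatment bears on persistence. That is fair. However, the visible text specifies no analysis of that assessment for carryover. The table of procedures and the grant proposal are not shown, so the finding covers the visible text only.

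A third is that the figures rest on assumed values, and that the other covariates named in the plan could change precision in either direction. This also stands: the figures describe the sequence contrast without those covariates. Within the stated range, no value brings the sequence test near reliable detection of a carryover of 0.5 SD.

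A reader might infer that the investigators intend to treat a null sequence effect as proof of an adequate washout. The documents state no such rule; they simply do not exclude that reading. A reader might also point out that carryover is estimated less precisely than the treatment effect. That is true of any crossover of this type with positive within-person correlation, whatever its size, so it is no defect of this plan.

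**Conclusion.** The concern holds as a matter of wording and of one analysis detail. As visibly specified, the study can estimate carryover but cannot be relied on to detect it. The 95% CI half-width is about 1.3–1.6 SD, with power of about 10–12% at 0.5 SD and 24–32% at 1 SD. With baseline adjustment the half-width is about 1.25–0.85 SD, and simulated power is about 12–21% and 35–63%. These results rest on the assumptions listed with the calculation; the split and the absence of dropout are favourable to the plan.

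Severity is minor. It would go too far to conclude that the crossover is invalid, that one week of washout is inadequate, or that the pilot needs a sample powered for carryover. A feasibility study does not need that power, and the documents give no estimate of carryover from which to judge the washout.

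**What to change.** 1. In the SA2 sentence, replace the claim of being able to detect carryover with a statement that the study *will estimate, with a 95% CI,* potential carryover effects.
2. In the analysis plan, adjust the sequence contrast for the pre-randomisation baseline score of the same outcome.
3. Add one sentence: a non-significant sequence effect will not be taken as evidence that the one-week washout or the crossover design is adequate.

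The cost is two sentences and one covariate, which uses one degree of freedom. No new visit, measurement or participant is needed, since baseline questionnaires are already planned. The stated aim becomes more modest and there is slightly more analysis to do. Item 2 improves precision but does not make carryover reliably detectable, so items 1 and 3 are needed with it.

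### The crossover mixed models have no period effect, so a shift between the two treatment blocks enters the BLT-sham estimate and its standard error

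*Combined protocol and SAP*

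**What the plan says.** The design is a two-sequence, two-period crossover with a one-week wash-out (View 2, Design Overview). The main model is set out in View 4.1, item 1.0, under SA1. The dependent variables are functional impairment and depression, with "treatment block (BLT vs. sBLT) as predictor of interest, treatment sequence as a covariate, and subject intercept as a random effect". The parenthesis defines treatment block as BLT versus sham, so that term is the treatment factor and not first versus second block.

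A further list follows: "Covariates we will be assessing include demographics (age, sex, race), comorbid conditions, lifestyle behaviors (smoking, alcohol use, substance use), adherence to BLT treatment", then CPAP adherence, medications and healthcare use. It has no period, visit or time term. The SA2 and SA3 paragraphs each end with the same sentence: "We will conduct multi-level mixed effects models of each outcome while adjusting for covariates as listed in the primary aim".

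SA1 also proposes to describe the "time course of treatment effects (e.g. do carry-over effects require a longer wash out period" and whether a parallel-group design would suit better. On allocation, View 6, item 2.0 says only that "The order of treatment is randomly assigned". Item 1.0 there caps enrolment at 25, and item 4.0 declines a power-based sample size.

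**The concern.** In a 2×2 crossover, period is the treatment-by-sequence interaction. A model with treatment and sequence main effects leaves it out. Sequence explains differences between people, whereas a change from the first to the second block is within-person.

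Any such change, for example from season or drift in CPAP use, therefore has two effects. It enters the BLT-sham estimate in proportion to the imbalance between sequences, and it inflates the residual variance. If all 25 places are filled and analysed, an exactly equal split is impossible. Dropout in the second block can create imbalance even where randomisation did not.

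At stake are the BLT-sham estimates and intervals the trial reports. View 2, item 3.0 says "we will have generated preliminary data critical to the design and implementation of a larger trial investigating the impact of BLT", and View 6, item 4.0 says "The statistics and qualitative data obtained from the proposed pilot trial will be used to inform design adjustments in the subsequent large trial". Neither names an effect size, a variance or a sample-size calculation, so harm to the sizing of a later trial is possible but not shown.

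**Working it through.** The plan has no power or error-rate figure to reproduce.

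**Inputs.** From the documents: the model terms, the two-by-two design and the maximum N = 25. Assumed: complete data, SD of the within-person BLT-sham difference = 1, and a block shift π (second minus first) of 0.25 or 0.5 on that scale. Allocation is treated as 1:1 with unspecified blocking, and splits from 13/12 to 17/8 are examined.

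**Bias.** Let τ be the true effect, n₁ the number BLT-first and n₂ the number sham-first. The within-person difference has mean τ − π in BLT-first and τ + π in sham-first. With complete data, the planned base model returns the mean paired difference, so its expectation given the split is

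τ + π(n₂ − n₁)/N.

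In 40 simulated 16/9 data sets, the mixed model with treatment, sequence and a random intercept matched the paired mean to within 3e-16. In one simulated data set with 10 BLT-first and 15 sham-first, the treatment estimate was 0.551 with or without sequence and 0.282 once period was added.

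At 17/8, (n₂ − n₁)/N is 9/25 = 0.36 in size, so π = 0.5 gives 0.36 × 0.5 = 0.18. With π > 0 the bias is negative if BLT-first is the larger group and positive if sham-first is.

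**Standard error and type I error.** Given the split, the paired mean has variance 1/N. The sum of squares is noncentral chi-square with 24 df and noncentrality 4n₁n₂π²/N, so the expected reported variance is

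(1/N) × [1 + 4n₁n₂π²/(24N)].

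This exceeds 1/N for any nonzero π. At 13/12 with π = 0.5 the noncentrality is 4 × 156 × 0.25/25 = 6.24, and the variance is inflated by 6.24/24 = 26%. Type I error comes from numerical integration and agreed with 200,000 simulated trials per scenario to within about 0.1 percentage point.

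**RMSE.** Planned model: √[1/N + bias²]. Period-adjusted: √[N/(4n₁n₂)].

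| Split | Size of bias, π 0.25 / 0.5 | Type I error, π 0.25 / 0.5 | RMSE plan vs adjusted, π 0.25 | RMSE plan vs adjusted, π 0.5 |
|---|---|---|---|---|
| 13/12 | 0.01 / 0.02 | 4.4% / 3.0% | 0.200 vs 0.200 | 0.201 vs 0.200 |
| 15/10 | 0.05 / 0.10 | 5.0% / 4.9% | 0.206 vs 0.204 | 0.224 vs 0.204 |
| 16/9 | 0.07 / 0.14 | 5.6% / 6.9% | 0.212 vs 0.208 | 0.244 vs 0.208 |
| 17/8 | 0.09 / 0.18 | 6.4% / 9.85% | 0.219 vs 0.214 | 0.269 vs 0.214 |

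The period-adjusted test stayed at 4.9–5.0% throughout. The mean reported SE under the plan is 0.204 / 0.222 at 13/12 and 0.203 / 0.219 at 17/8 (π 0.25 / 0.5), against a sampling SD of 0.200. Near balance the cost is therefore an inflated SE and a conservative test. At larger imbalance the bias dominates and the test becomes anti-conservative.

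**Likelihood of imbalance.** Under unblocked 1:1 allocation, Binomial(25, 0.5) gives a split of 15/10 or worse with probability 42%, 16/9 or worse 23%, and 17/8 or worse 11%.

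**Dropout.** With 12 BLT-first and 13 sham-first, and second-block dropout of 30% in BLT-first and none in sham-first, simulation gave a bias of about 0.12π, against 0.04π with complete data.

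**The case against.** The strongest reply is that the planned estimator is valid under either plausible allocation scheme. Under unblocked 1:1 randomisation its bias averages to zero, and type I error over all splits is 5.00% at π = 0.25 and 5.01% at π = 0.5. Under blocking the bias is near zero. The documents give no reason to expect a shift of any particular size. The 9.85% figure needs both π = 0.5 and a 17/8 split. At π = 0.25 the RMSE gain from adjustment is only 0–2%. Averaged over unblocked allocation, adjustment is slightly worse at π = 0.1 (RMSE 0.2045 against 0.2010).

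The stakes are also low. View 6, item 4.0 says "This study is mainly aimed at testing feasibility of the proposed design and intervention, rather than hypothesis testing through inferential statistics", SA2 and SA3 are labelled exploratory, and no alpha or decision rule is stated. Describing the time course is a feasibility item not assigned to the mixed model, and a period term would not settle the wash-out question.

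All of this stands and limits the weight of the point. It does not answer the conditional argument: the trial will report one known split, and under blocking the inflated SE remains. The plan also presents these models as its main outcome analyses.

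One further limit holds. Adherence to BLT or CPAP may vary by block, and once such a covariate is added the estimate need not equal the paired mean. The sizes above therefore apply to the base model. The covariate-adjusted models still omit period, but the size of their bias may differ.

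**Conclusion.** The concern holds. The SA1 model and the SA2 and SA3 mixed models that reuse its covariates omit period. The bias, conditional on the realised split, is exactly π(n₂ − n₁)/N for the base model with complete data: from 4% of the shift at 13/12 to 36% at 17/8. Whether that matters in practice depends on π, the SD of the difference and the allocation method, none of which is stated. Nothing is claimed about the repeated measures ANOVA or the Friedman tests, whose factors are not listed. The matter should be fixed because the remedy is cheap and standard; it does not threaten the feasibility aim.

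**What to change.** Add period (first versus second 4-week block) as a fixed effect in every SA1, SA2 and SA3 mixed model: outcome ~ treatment + period + sequence + (1 | subject). Report the period-adjusted estimates, with their residual variance, as the BLT-sham results. This also yields an estimate of the change between blocks, which the planned model does not give.

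The cost is one model term, a line of analysis-plan text and one residual degree of freedom (24 to 23 at N = 25), with no new data. If there is no period effect, the confidence interval widens by about 0.3% at 13/12, 2.3% at 15/10, 4.4% at 16/9 and 7.4% at 17/8.

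Adjustment lowers RMSE only when |π| exceeds √[N/(4n₁n₂)], which is 0.20 SD of the difference at 13/12 and 0.21 at 17/8. Below that it costs a little precision, and the adjusted SE can be the larger one (at 17/8 with π = 0.25, a mean of 0.212 against 0.203). It does not remove unequal carryover, which stays aliased with sequence.
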